6.3. Procedures During the Study Conduct Phase

The following examinations and assessments, etc. will be performed and the results will be recorded in the case report form. The details of the procedures are the same as those described in “[Section 6.2 Study Procedures before Registration of Subjects](#).”

6.3.1. Subtrial A (14/28 Day Schedule)

1. Confirmation of treatment compliance

- Whether to have taken the drug or not
- Date of administration
- Time of administration
- Dose (mg/day)
- Whether or not the study treatment was interrupted or postponed, or the dose was reduced, and if there was any intervention, the details and reason.

2. Vital signs measurement

When screening tests are performed within 24 hours before the first dose of the study drug, the tests before administration on Day 1 of Cycle 1 are not necessary.

Cycle 1	Day 1	Pre-dose and 3 h post-dose (± 10 min)
	* Day of the first dose of the study drug	
	Day 2	Pre-dose
	Day 8 (± 2 days)	Pre-dose
	Day 14	Pre-dose and 3 h post-dose (± 10 min)
	Day 22 (± 2 days)	Specified day
Cycle 2	Day 1	Pre-dose
	Day 14 (-4 days)	Pre-dose
Cycle 3 and thereafter	Day 1 (-4 days)	Pre-dose

3. Body weight measurement, ECOG PS assessment

When screening tests are performed within 24 hours before the first dose of the study drug, the tests before administration on Day 1 of Cycle 1 are not necessary.

Cycle 1	Day 1	Pre-dose
	* Day of the first dose of the study drug	
	Day 8 (± 2 days)	Pre-dose
	Day 14	Pre-dose
	Day 22 (± 2 days)	Specified day
Cycle 2	Day 1	Pre-dose
	Day 14 (-4 days)	Pre-dose
Cycle 3 and thereafter	Day 1 (-4 days)	Pre-dose

4. 12-lead ECG

Cycle 1	Day 1	Pre-dose and 3 h post-dose (± 10 min)
	* Day of the first dose of the study drug	
	Day 2	Pre-dose
	Day 8 (± 2 days)	Pre-dose
	Day 14	Pre-dose and 3 h post-dose (± 10 min)
	Day 22 (± 2 days)	Specified day
Cycle 2	Day 1	Pre-dose
	Day 14 (-4 days)	Pre-dose
Cycle 3 and thereafter	Day 1 (-4 days)	Pre-dose

5. Laboratory tests

For clinical laboratory parameters, the reference range of the institution that performs the measurements will be used. When screening tests are performed within 24 hours before the first dose of the study drug, the tests before administration on Day 1 of Cycle 1 are not necessary.

Cycle 1	Day 1	Pre-dose
	* Day of the first dose of the study drug	
	Day 2	Pre-dose
	Day 8 (± 2 days)	Pre-dose
	Day 14	Pre-dose
	Day 22 (± 2 days)	Specified day
Cycle 2	Day 1	Pre-dose
	Day 14 (-4 days)	Pre-dose
Cycle 3 and thereafter	Day 1 (-4 days)	Pre-dose

6. Pregnancy test

A urine or serum pregnancy test will be performed in female subjects.

A pregnancy test is not necessary in women who have been amenorrheic for at least 12 months after the last menstruation and who are considered to have no childbearing potential, or women who are not of childbearing potential after permanent surgical sterilization, etc. In this case, the information and reason will be recorded in the case report form.

A pregnancy test must be performed in women who have been amenorrheic for at least 12 months for medical reasons other than surgical sterilization (eg, medication) because they are considered to have childbearing potential.

Cycle 3	Day 1 (-4 days)	Pre-dose
---------	-----------------	----------

7. Evaluation method of the antitumor effect

Assessment will be made based on bone marrow findings and peripheral blood results (neutrophil count, platelet count, and number of blasts) in accordance with “[Section 10.1 Definition of Efficacy Endpoints](#).”

It is desired to obtain bone marrow specimens by bone marrow aspiration and biopsy. If the investigator or subinvestigator considers that the antitumor effect of DS-3032b can be assessed adequately using specimens obtained by bone marrow aspiration only, bone marrow biopsy may be skipped.

Cycle 2 and thereafter	Day 25 of the previous cycle to pre-dose on Day 1 of the present cycle * After CR is achieved, assessment based on bone marrow findings may be skipped until blasts are observed in the peripheral blood.
------------------------------	---

8. Confirmation of concomitant drugs and therapies

- Concomitant drugs and therapies

The following information on concomitant drugs and therapies other than the study drug, which are used during the period from the day of the first dose of the study drug to the visit day of the Follow-up period will be confirmed. As for concomitant drugs or therapies that are newly started after the following day of the last dose of the study drug, those used only for the treatment of AEs will be confirmed as to the following information.

- Name of drug (therapy), dose, unit, mode of administration, and dosage
- Start and end dates of drug (therapy)
- Reason for use (application)

The following items need not to be recorded in the case report form, except when a relationship between the AEs occurring in subjects during their participation in the study and the study drug cannot be ruled out:

- Antiseptic solutions

- Heparin for heparin lock flush
- Test drugs or treatment drugs used for tests including bone marrow aspiration or biopsy

- Transfusion

The following information on transfusion that is introduced during the period from the day of the first dose of the study drug to the visit day of the Follow-up period will be confirmed. As for transfusion that is newly started after the following day of the last dose of the study drug, only cases of use for the treatment of AEs will be confirmed for the following information.

- Type of blood products (whole blood, red blood cells, plasma, platelets, others)
- Start date, end date, amount of use (unit)
- Reason for use

9. Assessment of AEs

10. Collection of specimens for pharmacokinetic assessment and the biomarker study

Refer to “Section 6.7 Pharmacokinetics” and “Section 6.8 Biomarker Study”

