6.4. Procedures at Study Discontinuation

The investigator or subinvestigator will perform the following examinations and assessments, etc. on the day when discontinuation of the study is determined (± 3 days).

If the study is discontinued after 25 days from the last dose of the study drug with the day of the last dose set as 0 for any reason, examinations and assessments, etc. specified in this section will be omitted, and examinations and assessments, etc. presented in “Section 6.5 Examination Items during the Follow-up Period and the Time Points” will be performed immediately instead.

The details of the procedures are the same as those described in “Section 6.2 Study Procedures before Registration of Subjects” and “Section 6.3 Procedures During the Study Conduct Phase.”

- Date of discontinuation of the study and reason for discontinuation
- Vital signs measurement
- Body weight measurement
- ECOG PS assessment
- 12-lead ECG measurement
- Laboratory tests
- Assessment of bone marrow findings (It is desired to obtain bone marrow specimens by bone marrow aspiration and biopsy. If the investigators consider that the antitumor effect of DS-3032b can be assessed adequately using specimens obtained by bone marrow aspiration only, bone marrow biopsy may be skipped.)
- Confirmation of concomitant drugs and therapies
- Assessment of AEs
- Collection of biomarker specimens (blood and bone marrow)

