9.1. Definition of Adverse Events

An AE is any untoward or unintended sign (including an abnormal change in laboratory data or vital signs), symptom, or disease noted in subjects who received the study drug, whether it is considered to be related to the study drug or not.

A symptom or disease preexisting before the start of study treatment will be handled as a complication, not as an AE. However, complications that have worsened during the study treatment will be handled as AEs, and the date when worsening is confirmed will be used as the date of onset of the relevant event.

It is the responsibility of investigators, based on their knowledge and experience, to determine those circumstances or abnormal laboratory data which should be considered as AEs.

Progression of the primary disease (AML) will be handled as follows:

- Tumor progression will not be considered as an AE. However, if tumor progression results in death during the AE collection period, it will be handled as an SAE (this should be recorded as “disease progression” for the event term and “fatal” for the outcome).
- Worsening of signs or symptoms resulting from tumor progression will be handled as AEs.

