10.1. Definition of Efficacy Endpoints

The response criteria are defined as follows.

Table 10.1.1: Definition of Efficacy Endpoints

Complete remission: CR*	Bone marrow blasts <5%, neutrophil count $\geq 1000 / \text{mm}^3$, and platelet count $\geq 100,000 / \text{mm}^3$ in the absence of RBC or platelet transfusion (4 weeks for RBC transfusion, 1 week for platelet transfusion); absence of Auer rods; absence of extra-medullary leukemia. Absence of peripheral blasts.
CR with incomplete hematological recovery: CRI	All CR criteria are met, except for neutrophil count $< 1000 / \text{mm}^3$ and platelet count $\geq 100,000 / \text{mm}^3$ or neutrophil count $\geq 1000 / \text{mm}^3$ and platelet count $< 100,000 / \text{mm}^3$.
CR with partial hematological recovery: CRh**	All CR criteria are met, except for neutrophil count $> 500 / \text{mm}^3$ and platelet count $> 50,000 / \text{mm}^3$.
Partial remission: PR	Neutrophil count $\geq 1000 / \text{mm}^3$ and platelet count $\geq 100,000 / \text{mm}^3$ in the absence of RBC or platelet transfusion (4 weeks for RBC transfusion, 1 week for platelet transfusion); decrease in bone marrow blast percentage by at least 50% and total bone marrow blast percentage of 5% to 25%.
Morphologic leukemia-free state: MLFS	Bone marrow blasts <5% in the absence of blasts with Auer rods; absence of extra-medullary leukemia. The presence/absence of hematological recovery or blood transfusion is not considered.
Stable disease: SD	Absence of CR, CRI, CRh, PR, or MLFS; and criteria for PD not met.
Progressive disease: PD	When any of the following apply: ≥ 1.5 -fold increase in bone marrow blasts over baseline (eg, increase in blast count from 35% to $> 52.5\%$). At least 15% point increase in bone marrow blasts in cases with <30% blasts at baseline (eg, increase in blast count from 20% to 35%). Persistent bone marrow blast percentage of $> 70\%$ over at least 3 months. Cases with improvement in neutrophil count to $\geq 500 / \text{mm}^3$ and/or improvement in platelet count to $\geq 50,000 / \text{mm}^3$ (without transfusion) are excluded. ≥ 1.5 -fold increase in peripheral blasts (WBC \times % blasts) to $> 25,000 / \text{mm}^3$, in the absence of differentiation syndrome. New extra-medullary leukemia.
Relapse	Relapse after CR, CRI, or CRh (except in case the criteria for MLFS are also met): Either of appearance of peripheral blasts, bone marrow blast percentage $\geq 5\%$, or relapsed or new extra-medullary leukemia.

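### For a response first seen after the final dose, the case report form cannot confirm the transfusion-free condition of CR and PR, because transfusions newly started by then are recorded only if they treat an AE

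*Combined protocol and SAP*

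**What the plan says.** **Recording.** Item 8 of section 6.3.1 first covers all "transfusion that is introduced during the period from the day of the first dose of the study drug to the visit day of the Follow-up". It then narrows this: for transfusions "newly started after the following day of the last dose of the study drug, only cases of use for the treatment of AEs" are confirmed. Sections 6.3.2 to 6.3.4 carry the same rule. Section 6.4 refers back to 6.3 for its details, and neither 6.4 nor 6.5 adds any transfusion recording.

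**What counts as an AE.** Section 9.1: "A symptom or disease preexisting before the start of study treatment will be handled as a complication, not as an AE". A complication that worsens on treatment does become an AE.

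**Response definitions (Table 10.1.1).** CR and PR need neutrophil and platelet recovery "in the absence of RBC or platelet transfusion (4 weeks for RBC transfusion, 1 week for platelet transfusion"). CRi and CRh are both introduced by "All CR criteria are met, except for neutrophil count", followed by count thresholds. For MLFS, "The presence/absence of hematological recovery or blood transfusion is not considered". CRc is CR + CRi + CRh and the response rate is CRc + PR, so MLFS is in neither.

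**When response is assessed.** The scheduled marrow falls from "Day 25 of the previous cycle to pre-dose on Day 1 of the present cycle". A marrow is also taken at discontinuation (section 6.4). If discontinuation comes more than 25 days after the last dose, it is taken instead at Follow-up, day 30 ± 5 (section 6.5). Section 10.2 takes best response over all time points after the start of treatment, with no cut-off at the last dose.

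**The concern.** The response definition looks back 4 weeks for RBC and 1 week for platelets, while the recording rule becomes selective from the second day after the last dose. A marrow taken after that point is judged against a look-back period in which some disqualifying transfusions need not be recorded.

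The transfusions at issue are those that do not treat an AE: support for leukemic cytopenia that was present at baseline and has not worsened, and prophylactic transfusion. Such subjects can be enrolled, because inclusion criterion 6 in section 4.1.1 sets no minimum hemoglobin, neutrophil or platelet count.

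At stake is whether the CRc rate and the response rate, for which section 11.4.3 plans point estimates and 95% confidence intervals, can be checked from the study database. A missing transfusion can only make a subject appear to satisfy the condition. An undetected error would therefore be favourable: CR in place of MLFS, for instance, or PR in place of SD. A plausible case is a subject whose blasts clear during the final cycle and who then stops to go to transplant; section 6.6 lists HSCT among the subsequent treatments.

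**Working it through.** The plan gives no figure on this point, so there is none to reproduce. The check counts look-back days under reason-limited recording.

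**Inputs.**
- Look-back W: 28 days for RBC and 7 for platelets (Table 10.1.1).
- Last dosing day L in the final cycle: A 14, B 7, C 17, D 21 (section 3).
- First reason-limited day: L + 2 (item 8).
- Marrow day: M.

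**Formula, counting the assessment day.** Reason-limited days = min(W, M − (L + 2) + 1) = min(W, M − L − 1).

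| Marrow | RBC, of 28 | Platelet, of 7 |
|---|---|---|
| Subtrial A, Day 28, no further cycle | 28 − 14 − 1 = 13 | 7 |
| Subtrial B, Day 28, no further cycle | 28 − 7 − 1 = 20 | 7 |
| Subtrial C, Day 28, no further cycle | 28 − 17 − 1 = 10 | 7 |
| Subtrial D, Day 28, no further cycle | 28 − 21 − 1 = 6 | 6 |
| Discontinuation visit, 25 days after last dose | 25 − 1 = 24 | 7 |
| Follow-up marrow, 30 days after last dose | min(28, 29) = 28 | 7 |

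Leaving the assessment day out of the look-back lowers most RBC counts by one (12 for Subtrial A at Day 28, 23 at 25 days); the day 30 count stays at 28. On these days AE-related transfusions are still recorded.

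**Which assessments are exposed.** If another cycle follows, the last dose moves later and the rest-period transfusions fall under full recording. Only marrows after the final dose are exposed: the end of the final cycle, discontinuation, or Follow-up when the withdrawal assessment was omitted. A subject with a valid response on an earlier marrow keeps it under section 10.2.

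**Effect of one misclassified subject.** Cohorts have 3 to 6 subjects (section 3.2), analyses are by dose and schedule group (section 11.1), and the study plans 9 to 24 subjects (section 11.6).
- Group of 6: 1/6 = 16.7 points.
- 9 subjects: 1/9 = 11.1 points.
- 24 subjects: 1/24 = 4.2 points.

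The plan names no interval method. Assuming exact (Clopper-Pearson) 95% limits, moving from 0/9 to 1/9 changes the interval from 0–33.6% to 0.3–48.2%. Moving from 0/24 to 1/24 changes it from 0–14.2% to 0.1–21.1%.

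**After the fix.** With all RBC and platelet transfusions recorded through the last response assessment, no look-back day after the last dose is reason-limited.

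**The case against.** A reader might infer that the recording rule itself causes transfused subjects to be scored as responders. The documents do not support that. Response is assessed at the site against Table 10.1.1 and entered as a category, as the table's footnotes show; nothing says it is derived from the transfusion log. The transfusion condition binds the assessor whatever item 8 asks to be recorded. A wrong score needs the site to overlook its own patient's transfusion.

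Nor is the response beyond verification. Hospital and medical records are source documents (section 15.11.1) and the sponsor has direct access to them (section 15.12). What cannot be done is to check the condition from the case report form alone.

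Four further points narrow the concern:

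- The limit applies to newly started transfusions. Support already under way on treatment can be read as still recorded; the wording is ambiguous.
- Cytopenia that worsens on treatment is an AE, and its transfusions are recorded. This route is not rare: section 1.4 reports thrombocytopenia in 35.1% and anaemia in 32.4% of subjects in U102.
- It is tempting to say that CRi and CRh carry the transfusion condition too. That is the literal reading, but the clause qualifies the counts in the CR row, and those counts are what CRi and CRh relax. On the other reading, some transfused subjects stay in CRc as CRi or CRh, and the effect on the CRc rate is smaller. CR and PR state the condition expressly, so the point does not depend on this.
- At an end-of-cycle marrow with another cycle still planned, the site has no reason to have narrowed its recording yet. The day counts above are therefore upper figures.

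Detail is also deferred to a separately prepared SAP (section 11) and to case report form guidance (section 15.10.2). Neither is in the text reviewed, so a transfusion check there cannot be excluded.

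These objections remove the claim of built-in bias and reduce the likely number of affected subjects. They do not remove the mismatch between the stated recording rule and the stated response definition.

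**Conclusion.** The mismatch stands, as a minor data-capture point held with moderate confidence. For a response first seen at a marrow after the final dose, the collected data need not show whether the transfusion-free condition of CR or PR was met. Mis-scoring is possible, not demonstrated, and would go in the drug's favour.

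The exposure is narrow. It takes a first response at a post-treatment marrow, a newly started transfusion inside the look-back that treats no AE, and an oversight at the site. The documents give no basis for estimating how often this would happen. Subjects who leave for progression do not add to it, so few are likely to be affected. With groups of at most about 6, though, a single case is visible in the rate.

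Efficacy is a secondary objective, evaluated exploratively (section 2). DLT assessment and MTD determination are unaffected.

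The conclusion assumes that item 8 is applied as written and that no other form collects transfusions for the response assessment. The day counts assume that the final cycle's dosing was completed on schedule.

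**What to change.** In item 8 of sections 6.3.1 to 6.3.4, require all RBC and platelet transfusions to be recorded with dates, whatever the reason, through the subject's last bone marrow/response assessment, including one at discontinuation or Follow-up. Keep the AE-only limit after that point.

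The cost is one sentence in each of four sections and a matching change to the case report form guidance. Type, dates and reason are already collected, so no new fields are needed and clinical management does not change. The downside is a few extra transfusion entries for subjects off treatment.

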6.3.2. Subtrial B (7/28 Day Schedule)

1. Confirmation of treatment compliance
 - Whether to have taken the drug or not
 - Date of administration
 - Time of administration
 - Dose (mg/day)
 - Whether or not the study treatment was interrupted or postponed, or the dose was reduced, and if there was any intervention, the details and reason.

2. Vital signs measurement

When screening tests are performed within 24 hours before the first dose of the study drug, the tests before administration on Day 1 of Cycle 1 are not necessary.

Cycle 1	Day 1	Pre-dose and 3 h post-dose (± 10 min)
	* Day of the first dose of the study drug	
	Day 2	Pre-dose
	Day 7	Pre-dose and 3 h post-dose (± 10 min)
	Day 15 (± 2 days)	Specified day
	Day 22 (± 2 days)	Specified day
Cycle 2	Day 1	Pre-dose
	Day 7 (-2 days)	Pre-dose
	Day 22 (± 2 days)	Specified day
Cycle 3 and thereafter	Day 1 (-4 days)	Pre-dose

3. Body weight measurement, ECOG PS assessment

When screening tests are performed within 24 hours before the first dose of the study drug, the tests before administration on Day 1 of Cycle 1 are not necessary.

Cycle 1	Day 1	Pre-dose
	* Day of the first dose of the study drug	
	Day 7	Pre-dose
	Day 15 (± 2 days)	Specified day
	Day 22 (± 2 days)	Specified day
Cycle 2	Day 1	Pre-dose
	Day 7 (-2 days)	Pre-dose
	Day 22 (± 2 days)	Specified day
Cycle 3 and thereafter	Day 1 (-4 days)	Pre-dose

4. 12-lead ECG measurement

Cycle 1	Day 1	Pre-dose and 3 h post-dose (± 10 min)
	* Day of the first dose of the study drug	
	Day 2	Pre-dose
	Day 7	Pre-dose and 3 h post-dose (± 10 min)
	Day 15 (± 2 days)	Specified day
	Day 22 (± 2 days)	Specified day
Cycle 2	Day 1	Pre-dose
	Day 7 (-2 days)	Pre-dose
	Day 22 (± 2 days)	Specified day
Cycle 3 and thereafter	Day 1 (-4 days)	Pre-dose

5. Laboratory tests

For clinical laboratory parameters, the reference range of the institution that performs the measurements will be used. When screening tests are performed within 24 hours before the first dose of the study drug, the tests before administration on Day 1 of Cycle 1 are not necessary.

Cycle 1	Day 1	Pre-dose
	* Day of the first dose of the study drug	
	Day 2	Pre-dose
	Day 7	Pre-dose
	Day 15 (± 2 days)	Specified day
	Day 22 (± 2 days)	Specified day
Cycle 2	Day 1	Pre-dose
	Day 7 (-2 days)	Pre-dose
	Day 22 (± 2 days)	Specified day
Cycle 3 and thereafter	Day 1 (-4 days)	Pre-dose

6. Pregnancy test

A urine or serum pregnancy test will be performed in female subjects.

A pregnancy test is not necessary in women who have been amenorrheic for at least 12 months after the last menstruation and who are considered to have no childbearing potential, or women who are not of childbearing potential after permanent surgical sterilization, etc. In this case, the information and reason will be recorded in the case report form.

A pregnancy test must be performed in women who have been amenorrheic for at least 12 months for medical reasons other than surgical sterilization (eg, medication) because they are considered to have childbearing potential.

Cycle 3	Day 1 (-4 days)	Pre-dose
---------	-----------------	----------

7. Evaluation method of the antitumor effect

Assessment will be made based on bone marrow findings and peripheral blood results (neutrophil count, platelet count, and number of blasts) in accordance with “[Section 10.1 Definition of Efficacy Endpoints](#).”

It is desired to obtain bone marrow specimens by bone marrow aspiration and biopsy. If the investigator or subinvestigator considers that the antitumor effect of DS-3032b can be assessed adequately using specimens obtained by bone marrow aspiration only, bone marrow biopsy may be skipped.

Cycle 2 and thereafter	Day 25 of the previous cycle to pre-dose on Day 1 of the present cycle * After CR is achieved, assessment based on bone marrow findings may be skipped until blasts are observed in the peripheral blood.
------------------------------	---

8. Confirmation of concomitant drugs and therapies

- Concomitant drugs and therapies

The following information on concomitant drugs and therapies other than the study drug, which are used during the period from the day of the first dose of the study drug to the visit day of the Follow-up period will be confirmed. As for concomitant drugs or therapies that are newly started after the following day of the last dose of the study drug, those used only for the treatment of AEs will be confirmed as to the following information.

- Name of drug (therapy), dose, unit, mode of administration, and dosage
- Start and end dates of drug (therapy)
- Reason for use (application)

The following items need not to be recorded in the case report form, except when a relationship between the AEs occurring in subjects during their participation in the study and the study drug cannot be ruled out:

- Antiseptic solutions
- Heparin for heparin lock flush
- Test drugs or treatment drugs used for tests including bone marrow aspiration or biopsy

- Transfusion

The following information on transfusion that is introduced during the period from the day of the first dose of the study drug to the visit day of the Follow-up period will be confirmed. As for transfusion that is newly started after the following day of the last dose of the study drug, only cases of use for the treatment of AEs will be confirmed for the following information.

- Type of blood products (whole blood, red blood cells, plasma, platelets, others)
- Start date, end date, amount of use (unit)
- Reason for use

9. Assessment of AEs

10. Collection of specimens for pharmacokinetic assessment and the biomarker study

Refer to “Section 6.7 Pharmacokinetics” and “Section 6.8 Biomarker Study”

